 - d. eGFR < 45 mL/min/1.73 m² as determined by the Chronic Kidney Disease-Epidemiological Collaboration (CKD-EPI) equation for creatinine clearance OR serum creatinine > 1.8 mg/dL in males and > 1.5 mg/dL in females
 - e. Platelet count $< 125,000$ mm³
 - f. Abnormal thyroid function tests must be discussed with the Sponsor Medical Monitor or Designee
 - g. HbA1c $> 10\%$
 - h. Abnormal morning cortisol test demonstrating symptomatic adrenal insufficiency based on Investigator judgement
11. Active infection requiring systemic antiviral or antimicrobial therapy that will not be completed prior to Study Day 1
12. Unwillingness to comply with study procedures, including follow-up, as specified by this protocol, or unwillingness to cooperate fully with the Investigator
13. Active infection with human immunodeficiency virus (HIV), hepatitis C (HCV) or hepatitis B (HBV) diagnosed by initial serology testing and confirmed with RNA testing, or prior treatment for HCV. Patients at Screening who test positive by serology, but negative by RNA may be allowed in consultation with the Sponsor Medical Monitor or Designee
14. Malignancy within 5 years, except for basal or squamous cell carcinoma of the skin, carcinoma *in situ* of the cervix, follicular Stage 1 or papillary thyroid cancer that has been successfully treated; patients that have been treated with curative intent and which have

no recurrence within 5 years may also be eligible if approved by the Sponsor Medical Monitor or Designee

15. Treatment with another investigational drug, biological agent, or device within 1 month of Screening, or 5 half-lives of investigational agent, whichever is longer
16. Treatment with any non-ION- or ISIS-oligonucleotide (including small interfering ribonucleic acid [siRNA]) at any time or prior treatment with an ION- or ISIS-oligonucleotide within 9 months of Screening. Patients that have previously received only a single-dose of an ION- or ISIS-oligonucleotide as part of a clinical study may be included as long as duration \geq 4 months has elapsed since dosing. This exclusion does not apply to vaccines (neither mRNA nor viral vector vaccines)
17. History of bleeding diathesis or coagulopathy
18. Recent history of, or current drug or alcohol abuse that could affect study compliance per Investigator judgment

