6.1.1. Screening

Written informed consent for the study will be obtained prior to the performance of any study-related procedures including screening procedures. Race and ethnicity data will be

collected as part of the demographic information for all screened patients during the Screening Period. Up to a 6-week Screening Period is provided for completing screening assessments and determining patient eligibility for the study.

During the 6 weeks, site will need to gather disease history relating to acromegaly and pituitary adenoma, and the results of the most recent MRI. MRI of the sellar will need to be performed before randomization if there is no prior MRI within the last 3 months prior to Screening. If the MRI is contraindicated, then a CT Scan may be performed. In addition, an echocardiogram will be conducted, if there is no prior echocardiogram within the last 3 months prior to Screening.

Individuals may be disqualified if the result of any laboratory test is outside the range specified in the eligibility criteria (Section 5.1 and 5.2) or, if no range is specified, is abnormal and CS as judged by the Investigator or the Sponsor Medical Monitor or Designee. During the Screening Period, screening results may be retested (Home Health Care Visit Option can be used) for assessment after discussion with the Sponsor Medical Monitor or Designee for eligibility purposes.

IGF-1 can be repeated once and averaged to determine eligibility if the initial result is between 1.1–1.3 × ULN, or between 5–5.3 × ULN.

Sponsor Medical Monitor or Designee review of eligibility is required for patients to enter the Treatment Period. Qualified patients will be randomized and proceed to the Treatment Period Week 1, Day 1 Assessments.

Screen failed patients may be re-screened 1 more time after the Investigator feels the reason for screen failure has resolved.

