Appendix A. Schedule of Procedures – Treatment Period Continued

Study Period	Screen ¹	Treatment Period ²																							
Study Week	-6 to -1	1	3	5	7	9	11	13	15	17	21	25	27	29	33	37	41	45	49	53	57	61	65	69	73
Study Day	-42 to -1	1	15	29	43	57	71	85	99	113	141	169	183	197	225	253	281	309	337	365	393	421	449	477	505
Visit Window ± Day	0		3	5	7	7	7	7	7	7	7	7	7	7	7	7	7	7	7	7	7	7	7	7	
Home Health Care Visit Option ¹⁶				X		X		X		X	X		X	X	X		X	X	X		X	X	X		
Immunogenicity Testing ¹⁴		X		X		X		X		X			X			X			X			X		X	
PK Blood Sampling ¹⁴		X ¹⁵	X	X		X		X		X ¹⁵	X	X	X	X	X	X	X	X	X	X	X	X	X		
Urinalysis	X	X	X	X	X	X	X	X	X	X	X	X	X	X	X	X	X	X	X	X	X	X	X		
ISIS 766720 Administration		X	X	X		X		X		X	X		X	X	X	X	X	X	X	X	X	X	X		
Patient Contact		If a visit cannot be conducted, patient contact (e.g., phone, text, email or video) is required by site personnel to assess Adverse Events and Concomitant Medications																							

ALL STUDY PROCEDURES ARE CONDUCTED PRIOR TO THE ISIS 766720 INJECTION, EXCEPT PK DAY 1 & DAY 113.

- ¹ During the Screening Period, screening results may be retested using the Home Health Care Visit Option for assessment after discussion with the Sponsor Medical Monitor or Designee for eligibility purposes
- ² If a patient terminates early from the Treatment Period, an early termination visit from treatment (ETTX) is required as soon as possible, preferably 4 weeks after the last dose. After ETTX visit, patient should continue in Post-Treatment Period, following the schedule in intervals relative to patient's last dose
- ³ Prior MRI/CT and/or echocardiogram (ECHO) performed within the last 3 months of screening visit can be used. The window to conduct the MRI at Day 365 (WK53) and Day 505 (WK 73) and ECHO at Day 505 (Week 73) is ± 2 weeks
- ⁴ Height collected at Screening only
- ⁵ BP, heart rate (HR), RR, temperature
- ⁶ Full PE to be given at Screening and abbreviated physical exam to be given during Treatment as indicated to assess changes from Screening

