Appendix A. Schedule of Procedures – Treatment Period Continued

Legend Continued

- ¹² The pre-dose Day 1 OGTT may be conducted during the Screening Period between Day -41 and pre-dose Day 1. To decrease the study burden on potential patients, it is suggested that this procedure is done after the patient has completed and qualified for all other screening procedures. The procedure can be conducted in the clinic or by a Home Health Care professional. The window for completing Day 183 and Day 505 OGTT is \pm 30 days
- ¹³ Stored at -70 (± 10) $^{\circ}\text{C}$ for follow-up exploration of laboratory findings and/or AEs (e.g., measurement of cytokine and/or chemokine levels, measurement of additional markers of kidney function, measurement of antibodies, etc.)
- ¹⁴ Unless otherwise specified, all PK and immunogenicity samples must be collected pre-dose
- ¹⁵ Pre-dose, 1, 2, 4 hours. See [Appendix C](#)
- ¹⁶ Home health may be used at these visits if applicable. In consultation with the Sponsor, a Home Health Care visit may be conducted for a study day visit that was intended to be a clinic visit; it is preferable that the entire visit is conducted, however the following assessments may be omitted: ECG, body weight, physical exam, ring size, and OGTT. Any assessments not completed at the Home Health Care visit should be attempted at the next clinic visit. A confirmation of ISIS 766720 dosing by the Home Health Provider should be obtained and documented in source within 48 hrs

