3.6.4. Immunogenicity (IM) Analysis

Immunogenicity (IM) analyses will be conducted in the ‘Safety Set’. Samples collected for IM assessment at selected time points will be analyzed for anti-ISIS 766720 antibodies (i.e., anti-drug antibodies; ADA). Samples will be designated ‘IM positive’ based on both positive screening and confirmation assay results (i.e., confirmed positive result), otherwise they will be deemed ‘IM negative’. Study subjects will be given ‘positive’ subject IM status if they have at least one confirmed positive sample at any time during the Treatment or Post-treatment Evaluation Periods. Study subjects will be given ‘negative’ subject IM status if all evaluated IM sample results during the Treatment and Post-treatment Evaluation Periods are negative and they have at least one evaluable IM result post-dose. Otherwise, study subjects will be given ‘unknown’ subject IM status.

Sample IM status (screen positive/negative, confirmed positive/negative or not evaluable, and when applicable, titer of anti-ISIS 766720 antibodies) before, during, and after treatment with ISIS 766720 will be listed by the ISIS 766720 dose received (80 mg, 120 mg or 160 mg). Subject IM status (positive/negative or unknown) for all evaluable patients, along with the study day associated with the first positive IM status emerged (T_{first} , i.e., onset of ADA development), the last positive IM status observed (T_{last}) and max and/or end of treatment titer will be listed by treatment and dose.

Additionally, the sample and patient IM incidence (number) and incidence rate (percent) will be summarized as the total number and percent of evaluated patients with antibody negative, positive, and unknown status by the ISIS 766720 dose received (80 mg, 120 mg or 160 mg). Furthermore, onset, and peak titer of the ADA response, if applicable, will be summarized as median, interquartile range (25th percentile, 75th percentile), and range (minimum, maximum).

Other immunogenicity data analysis may be conducted at the discretion of the pharmacokineticist and/or statistician. Potential relationships between immunogenicity results (e.g., IM status) and selected efficacy (e.g., %change in serum IGF-1, GH, and GHBP levels), safety, and pharmacokinetic measures (e.g., C_{trough}) may be evaluated in an exploratory manner either in this report and/or combined with other ISIS 766720 clinical PK data later in the development timeline.

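### As worded, the SAP 3.6.4 rule for antibody-positive status counts a positive on the pre-dose Day 1 sample and dates its onset to Day 1

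*Combined protocol and SAP*

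**What the plan says.** SAP 3.6.4 (Immunogenicity Analysis) sets three subject-level categories.

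- **Positive:** "at least one confirmed positive sample at any time during the Treatment or Post-treatment Evaluation Periods".
- **Negative:** every evaluated sample in those two periods is negative and "they have at least one evaluable IM result post-dose".
- **Unknown:** everyone else.

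The study day of the first positive (T_first) is described as "i.e., onset of ADA development". Incidence is tabulated by dose received. Onset and peak titer are summarized by median, quartiles and range. Sample-level status before, during and after treatment is listed. SAP 3.6.1 plans trough-concentration plots both without and with stratification by this subject status, as applicable.

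The sampling times are in the protocol. Section 6.1.1 says that qualified patients are randomized and "proceed to the Treatment Period Week 1, Day 1 Assessments". In Appendix A, the row "Immunogenicity Testing" has its first mark at Week 1, Day 1 and none at Screening. Footnote 14 reads "Unless otherwise specified, all PK and immunogenicity samples must be collected pre-dose", and the note under the schedule reads "ALL STUDY PROCEDURES ARE CONDUCTED PRIOR TO THE ISIS 766720 INJECTION, EXCEPT PK DAY 1 & DAY 113".

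**The concern.** A statement that antibodies developed on drug needs a sample taken after drug. Here the only pre-drug sample falls inside the window that defines positive status, and nothing in the positive rule removes it or compares later samples with it. Pre-existing, treatment-emergent and treatment-boosted antibodies are not distinguished at subject level. The SAP does draw that line for adverse events: under Section 3.7.2 an event that began before dosing counts as treatment-emergent only if a linked later record is worse.

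Pre-existing reactivity cannot be ruled out. Exclusion criterion 16 bars earlier ION or ISIS oligonucleotide treatment only within 9 months of Screening, and "Patients that have previously received only a single-dose of an ION- or ISIS-oligonucleotide as part of a clinical study may be included" provided that at least 4 months have passed since dosing.

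At stake are the descriptive ADA incidence by dose, the onset and peak-titer summaries, the IM-stratified PK plots, and any exploratory comparison of IM status with IGF-1 response, safety or exposure.

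**Working it through.** The documents state no ADA rate, so there is no figure of the plan's own to reproduce. The check traces the rule through the schedule and then sizes the effect on stated assumptions.

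**Tracing the rule**

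1. Day 1 is the first Treatment Period visit (Protocol 6.1.1, Appendix A).
2. The Day 1 immunogenicity sample is taken before the first injection. Only PK on Days 1 and 113 is exempt from pre-injection collection (Appendix A, footnote 14 and the note under the schedule).
3. There is no Screening immunogenicity sample, so Day 1 is the only one before drug.
4. The positive rule accepts any confirmed positive in the Treatment Period, so by steps 1 and 2 it accepts this one. T_first is then Day 1.
5. The two rules treat the same sample differently. Take a patient whose only evaluable sample is Day 1 pre-dose:

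| Day 1 pre-dose result | Post-dose result | Status under SAP 3.6.4 |
|---|---|---|
| Negative | none | Unknown |
| Positive (confirmed) | none | Positive, T_first = Day 1 |

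**Effect of one patient on the planned table**

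Incidence is tabulated by dose. With 12 evaluable patients per group (SAP 3.3.3), one patient who is positive pre-dose and has no post-dose titer rise adds 1/12 = 8.3 percentage points. A patient who is positive pre-dose and also meets a titer-rise criterion would count under either rule, so the incidence does not change.

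**Effect on median onset (invented example)**

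If three patients first turn positive on Days 57, 85 and 113, the median onset is Day 85. Adding one pre-dose positive gives Days 1, 57, 85 and 113, with median (57 + 85)/2 = Day 71.

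**Chance that it happens at all (assumed rates)**

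For a pre-existing rate p, P(at least one in n) = 1 − (1 − p)^n.

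| Assumed p | Group of 12 | All 40 | Expected in 40 |
|---|---|---|---|
| 2% | 22% | 55% | 0.8 |
| 5% | 46% | 87% | 2.0 |
| 10% | 72% | 99% | 4.0 |

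**Mix among reported positives (assumed rates)**

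Suppose a fraction te = 20% of Day 1-negative patients convert. The reported rate is p + (1 − p) × te, and the pre-existing share is p divided by that.

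| Assumed p | Reported positive | Pre-existing share of positives |
|---|---|---|
| 2% | 0.02 + 0.98 × 0.20 = 21.6% | 9% |
| 5% | 0.05 + 0.95 × 0.20 = 24.0% | 21% |
| 10% | 0.10 + 0.90 × 0.20 = 28.0% | 36% |

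The rate among Day 1-negative patients is 20% in every row. Both p and te are assumptions; neither comes from the documents.

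**The case against.** The best reply is that this is loose drafting. SAP 3.6.4 never names the Day 1 sample; its inclusion follows only when the rule is read with Appendix A. The same section separates samples before treatment from those during and after it, and its language of emergence, onset and response fits post-dose positives better. The general baseline definition (Protocol 10.4; SAP 3.2.1 for endpoints other than IGF-1) already points to the last value before first dose. Status based on any confirmed positive is a coherent descriptive quantity in itself. A baseline positive could be recognized from the sample listing, from a T_first of Day 1, or from the minimum in the onset summary. The comparisons with efficacy and safety are optional, and no endpoint, analysis set, dosing rule or stopping rule uses IM status.

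Much of this stands, and it limits the point. A reader might infer that the plan intends to present pre-existing antibodies as drug-induced, or that the reported incidence will be wrong. The documents support neither. The first is an effect of the wording, with no sign of intent. The second depends on a patient being positive before dosing, and no rate is given. Exclusion 16 makes earlier oligonucleotide exposure possible but does not show that any such patient is expected, or that antibodies to another oligonucleotide would be confirmed in this assay. Nor does a figure on the whole trial, 1/40 = 2.5 to 1/30 = 3.3 points per patient, describe the planned table, which is by dose.

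The reply does not remove the defect. The baseline definition is not linked to subject IM status, and the post-dose condition appears only in the negative rule. Listings can reveal a case, but they do not correct an incidence, a median or a stratified plot.

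**Conclusion.** The point holds as a defect in a stated rule with a conditional effect. Taken literally, SAP 3.6.4 counts a confirmed pre-dose Day 1 positive towards positive status and dates onset to Day 1. If no patient is positive before dosing, nothing changes. If one is, and shows no post-dose titer rise, the incidence in a dose group of 12 is about 8 percentage points too high as a measure of treatment-emergent ADA, and a Day 1 value enters the onset summary.

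This rests on Day 1 belonging to the Treatment Period, as Protocol 6.1.1 and Appendix A have it, and on an immunogenicity denominator near the planned 12 per group. The affected outputs are descriptive or exploratory. The rule should be corrected before analysis, but it does not threaten the trial's main conclusions.

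**What to change.** In SAP 3.6.4:

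1. State that the SAP's general baseline definition applies to immunogenicity, so that the Day 1 pre-dose sample is the baseline.
2. Define treatment-emergent positive status as a confirmed positive post-dose sample in a baseline-negative patient. Base T_first, incidence, onset, peak titer and all IM-status strata, including the plots in SAP 3.6.1, on it.
3. Report baseline-positive patients in a separate row. Count them as treatment-boosted only if they meet a titer-rise criterion fixed in the SAP before analysis.
4. Say how a missing or non-evaluable Day 1 sample is classified, since no Screening sample can stand in for it.

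The cost is a few sentences of SAP text and slightly more programming. No new sample or visit is needed. The reported ADA incidence may be lower than under the present rule.

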3.7. Safety Analyses

The safety analysis will be conducted on the Safety Set. The results are summarized by the maximum ISIS 766720 dose received through the study and by overall.

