8.7. Adjustment of Dose and/or Treatment Schedule

ISIS 766720 dose adjustments and interruptions will be allowed for safety, tolerability or efficacy. Dose adjustments for efficacy (no higher than a 200 mg dose) may be made after Week 17 IGF-1 results are available. It is recommended to maintain an adjusted dose for efficacy for 3 months prior to further adjustment. Any dose adjustment requires consultation with the Sponsor Medical Monitor or Designee.

Patients may have their dose interrupted in response to AEs after consultation with Sponsor Medical Monitor or Designee.

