10.6.2. Safety Analysis

Treatment duration and amount of ISIS 766720 received will be summarized by treatment group and total. The TEAEs and serious TEAEs will be summarized for each treatment group and total using the Medical Dictionary for Regulatory Activities (MedDRATM) coding system, by system organ class, preferred term, relationship to ISIS 766720, and severity. Tables and/or narratives of treatment-emergent deaths, serious and significant AEs, including early withdrawals due to AEs, will also be provided.

Laboratory tests including chemistry panel, complete blood count with differential, coagulation panel, complement etc., will be summarized by study visits for each treatment group and total. These safety variables will also be presented as change and percent change from Baseline over time after ISIS 766720 administration, as appropriate. Vital sign, calculated BMI, and ECG measures will be summarized by treatment group and total. Concomitant medications will be coded using WHO Drug dictionary and summarized as well.

Echocardiograms will be assessed by an independent central reader. Change from baseline will be summarized for the following parameters, that may include left ventricular mass (LVM), LVM index (LVMi), LV ejection fraction, LV posterior wall thickness (LVPWT), peak velocity ratio (E/A), interventricular septum thickness (IVST) and isovolumic relaxation time (IVRT) whenever possible.

[figure not shown]

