3. ANALYTICAL PLAN

3.1. Statistical Design Summary

This is a Phase 2, randomized, open label multi-center study. Approximated 40 eligible patients will be randomized into one of the three treatment groups [REDACTED]

The primary endpoint is the percent change from Baseline to Week 27 in serum IGF-1 and analyzed by one-sample t-test with an alpha level of 5%. The statistical outcomes are summarized by the ISIS 766720 dose received [REDACTED] and overall.

Additional summary by the adjusted dose (refer to protocol Section 8.7) received may be provided.

An interim analysis may be conducted when approximately 50% of patients complete the primary efficacy assessment. The primary analysis will take place after all patients complete Treatment Period and the database has been locked.

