3.2. General Overview of Analyses

3.2.1. Statistical Methods

Descriptive summary statistics including number of patients, mean, median, standard deviation, standard error of mean, 25th percentile, 75th percentile, minimum, and maximum for continuous variables, and counts and percentages for categorical variables will be provided to summarize most data. The study outcomes will be summarized by treatment groups. The efficacy endpoints

will be assessed on the FAS and PPS with the latter being the basis for the primary efficacy analysis. The safety analyses will be performed on the Safety Set. Pharmacokinetic analysis will be conducted in the PK Set.

For the continuous outcomes, the data will be analyzed using one-sample t-test to evaluate the estimate percent changes are different than zero. For the categorical outcomes, the data will be analyzed by using one-sample binomial Exact test ([Clopper and Pearson 1934](#)) to evaluate whether the estimate proportions are deviated from zero. The normality assumption for one-sample t-test model will be assessed by the Shapiro-Wilk test. In the case of data departs substantially from normality, the nonparametric Wilcoxon signed rank test will be applied instead. All statistical tests will be conducted using 2-sided tests with 5% Type I error rate unless otherwise stated. Where appropriate, P-values will also be provided as an indicator to summarize how much deviation from zero within each treatment group based on the statistical tests.

Additional summary of between treatment group comparison may be provided. Treatment group and the stratification factor are included as the independent variables in the statistical model while comparing among treatment groups. For the continuous endpoints, the ANCOVA or ANOVA model will be applied depending on the independent variables or van Elteren test if the data departs substantially from normality. For the dichotomous endpoints, logistic regression will be used instead.

Additional subject listings included case report form (CRF) data and derived outcomes from the data may be presented.

Baseline definition:

Due to the variance of IGF-1 between Screening and Day 1, baseline of IGF-1 is defined as the average value of Screening and Day 1 prior to the first administration of ISIS 766720. Multiple results with the same visit label will be averaged first, and baseline IGF-1 will be calculated as IGF-1 at Screening plus IGF-1 at Day 1 divide by 2.

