3.3.2. Analysis of Primary Endpoint

The analysis of the study primary endpoint will be conducted in the PPS. The results will be summarized by the ISIS 766720 dose received at randomization and overall. In addition, because most of patients will have dose escalation after primary endpoint of Week 27, the results will also be summarized by the maximum ISIS 766720 dose received through the study and overall.

Subset analysis will be conducted among uncontrolled population ($IGF-1 > 1.3 \times ULN$ at Day 1) and high-strata IGF-1 population ($IGF-1 > 2.5 \times ULN$ at Screening), separately. The data will be analyzed using one-sample t-test to detect the reduction of IGF-1 significant different than zero at Week 27. The normality assumption for one-sample t-test model will be assessed by the Shapiro-Wilk test. In the case of data departs substantially from normality, the nonparametric Wilcoxon signed rank test will be applied instead. Additional summary in FAS will be provided.

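### SAP 3.7 tabulates safety only by maximum dose received, not by the treatment group that protocol 10.6.2 requires, so by-dose safety columns depend on what happened after randomisation

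*Combined protocol and SAP*

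**What the plan says.** SAP 3.7 sets the grouping for all safety results: "The results are summarized by the maximum ISIS 766720 dose received through the study and by overall". No safety table by randomised dose is named in SAP 3.7 or its subsections.

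Protocol 10.6.2 differs: "The TEAEs and serious TEAEs will be summarized for each treatment group and total". It uses the same grouping for exposure, laboratory tests, vital signs and ECG. SAP 3.2.1 has a general rule that agrees with the protocol: "The study outcomes will be summarized by treatment groups".

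Efficacy is handled differently. SAP 3.3.2 says "The results will be summarized by the ISIS 766720 dose received at randomization and overall" and adds maximum dose as a second grouping, "because most of patients will have dose escalation after primary endpoint of Week 27". SAP 3.4.2 does the same for the secondary endpoints.

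On dose changes, protocol 8.7 says "Dose adjustments for efficacy (no higher than a 200 mg dose) may be made after Week 17 IGF-1 results are available", and it also allows adjustments and interruptions for safety or tolerability. SAP 3.1 offers only an option: "Additional summary by the adjusted dose (refer to protocol Section 8.7) received may be provided". The grouping sentence just before that one is partly redacted.

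The SAP's Summary of Changes lists the move to maximum dose for safety, so it was deliberate. The list gives no reason specific to safety, and protocol 10.6.2 was left as it stands.

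**The concern.** Safety and tolerability form a primary objective in both documents, and by-dose safety columns are there to be read across doses. Maximum dose is a post-randomisation variable. To enter a higher column by escalation, a patient must still be on drug when the dose is raised. Two things follow.

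- **Events move up.** An event that began at the starting dose is counted under the higher dose reached later. This affects whole-study tables: TEAEs by worst severity (SAP 3.7.2) and worst confirmed platelet category (SAP 3.7.4). By-visit tables still show timing.
- **Early stoppers stay down.** A patient who stops before escalation remains in the column of the starting dose. This bears directly on the table of TEAEs leading to permanent discontinuation.

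A reader comparing columns could see a dose gradient that the grouping produced, or miss a real one.

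**Working it through.** **1. The plan's own design figure.** SAP 3.3.3 assumes a 27.5% reduction, SD 30%, and a 2-sided 5% one-sample t-test. The noncentral t distribution gives 82.4% power at n = 12 and 78.2% at n = 11, so 12 is the smallest n reaching 80%. Three groups give 36, and 36/(1 − 0.10) = 40. Both figures reproduce. This point does not depend on them; only the 10% drop-out is borrowed below.

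**2. Calendar (protocol 6.1.2, Appendices A and C).** There are 20 doses: Days 1, 15 and 29, then every 28 days from Day 57 to Day 505. Day 183 has no dose. The first dose after the Week 17 visit is nominally Day 141; the first after Week 27 is Day 197.

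| Before the first higher dose | Day 141 | Day 197 |
|---|---|---|
| Doses, of 20 | 6 (30%) | 8 (40%) |
| Treatment days, of 504 | 140 (28%) | 196 (39%) |
| Days to end of follow-up, of 603 | 140 (23%) | 196 (33%) |
| Treatment visits after Day 1, of 23 | 9 (39%) | 12 (52%) |

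The visit count includes the visit on the escalation day, because blood is drawn before dosing. Conversely, 14 or 12 of the 20 doses (70% or 60%) follow escalation, so whole-study columns by randomised group mix doses too.

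**3. Discontinuation with no true dose effect.** Assumptions, none fixed by the documents:

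- 10% all-cause discontinuation over the Treatment Period. SAP 3.3.3 gives 10% overall without a period, and no rate is given for discontinuation due to AEs.
- Constant hazard: h = −ln(0.9)/73 per week, S(t) = exp(−h·t), T = 72 weeks.
- A share p = 0.75 of those still on drug escalates at te = 20 weeks (Day 141) or 28 weeks (Day 197).
- Equal 120 and 160 mg arms and no 80 mg arm. A share s = 0.5 of 120 mg escalators reaches 160 mg and the rest reach 200 mg. All 160 mg escalators reach 200 mg.

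Write early = 1 − S(te) and late = 1 − S(T − te). Then:

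- Maximum 120: [early + S(te)(1−p)·late] / [early + S(te)(1−p)]
- Maximum 160: [early + S(te)(1−p)·late + S(te)·p·s·late] / [early + S(te)(1−p) + S(te)·p·s]
- Maximum 200: late

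At te = 28, early = 0.0396, S = 0.9604 and late = 0.0615. Maximum 120 is (0.0396 + 0.2401 × 0.0615)/(0.0396 + 0.2401) = 19.4%.

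| True rate 9.9% at every dose | 120 mg | 160 mg | 200 mg |
|---|---|---|---|
| Day 197, p = 0.75 | 19.4% | 12.0% | 6.2% |
| Day 141, p = 0.75 | 17.0% | 11.4% | 7.2% |
| Day 197, p = 0.60 | 14.9% | 11.4% | 6.2% |
| Day 141, p = 0.60 | 13.6% | 11.0% | 7.2% |

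**4. The 160 mg figure is fragile.** With equal arms and p = 0.75 it runs from 9.9% (s = 1) to 19.4% (s = 0) at Day 197, and from 9.9% to 17.0% at Day 141. With 2:1 arms (120:160 mg) and s = 1 it falls to 8.3% or 8.7%. The introduction to protocol Amendment 3 says allocation may not be equal, so no range built on equal arms is complete.

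**5. In patients.** With 30 patients (Day 197, p = 0.75, s = 0.5) the columns hold 4.2, 9.6 and 16.2. Expected discontinuations are 0.82, 1.15 and 1.00, against 0.41, 0.95 and 1.60 at the true rate. Each shift is below one patient.

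**6. TEAEs in general.** A simulation with an AE hazard independent of dose (20% or 40% incidence, 60% or 80% escalating) gave equal incidence by randomised arm throughout. By escalation status, incidence was equal if no AE stopped treatment. If 25–50% did, it was 21–30% in non-escalated against 17–19% in escalated patients (true 20%). Of first AEs in the escalated column, 14–38% began before escalation.

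**The case against.** The strongest reply is that nothing formal is at risk. No between-dose safety test is planned, the overall column is untouched, and the optional between-group comparison in SAP 3.2.1 uses treatment group. Listings of AEs leading to discontinuation, AESI and laboratory listings, and the protocol's tables or narratives for serious AEs and withdrawals give partial protection in so small a study. All of that stands, and it limits the severity.

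Randomised dose is not a clean grouping either. Its whole-study columns include time at adjusted doses, and because some countries lacked approval for some doses, allocation could depend on region. That also stands. It is a reason to add a table by dose at onset, not to drop the grouping the protocol asks for.

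Four stronger readings are not supported:

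- **The change is a slip.** The Summary of Changes records it as intended. What is missing is a safety rationale and agreement with the protocol.
- **All by-dose safety results are biased in one known direction.** That holds for discontinuations. For other TEAEs, moving early events up can oppose keeping early stoppers down. The simulation's single direction rests on a constant, dose-independent hazard that the documents do not give.
- **A 200 mg column is defined.** It is inferred from protocol 8.7; SAP 3.7 lists no columns, and Day 141 is nominal with a ±7-day window.
- **Every dose-grouped output is affected.** The immunogenicity summaries are grouped "by the ISIS 766720 dose received (80 mg, 120 mg or 160 mg" under SAP 3.6.4, separately from SAP 3.7.

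**Conclusion.** The point holds as a conflict between SAP 3.7 and protocol 10.6.2, and within the SAP between 3.7 and 3.2.1, with an avoidable distortion in the by-dose safety tables. This is said of the visible text, given the redaction in SAP 3.1.

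The calendar shares follow from the schedule and need only the nominal escalation day. The discontinuation percentages are an illustration: their size depends on the assumed 10%, 75%, escalation split and allocation ratio. Their direction does not, because a patient who has stopped cannot later be escalated. It should be fixed, but it does not undermine the overall safety summary, and by-dose figures from about 30 patients will be imprecise under any grouping.

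**What to change.** In SAP 3.7:

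1. Restore safety tables by randomised treatment group and total, as protocol 10.6.2 requires. Note that whole-study columns include time at adjusted doses and that allocation could depend on region.
2. Add TEAEs by dose in effect at onset, with person-time. The rule should cover increases, reductions and interruptions, and say that events soon after a change may reflect the previous dose.
3. Optionally show randomised-group results up to the first dose change as supportive. State that this cut is not random, since changes can follow IGF-1 response or tolerability, and use exposure-adjusted rates because time to the cut is unequal.
4. Keep the maximum-dose tables as a labelled supplement, and reconcile SAP 3.7 with protocol 10.6.2, giving the reason for any departure.

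The cost is SAP wording and a few extra tables with small columns. No new data are needed: dosing details are on the Dosing CRF (protocol 9.5.3), and AE start dates already define treatment emergence (SAP 3.7.2). None of this touches the dosing rules.
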